15.2. Documentation of data Case Report Forms (CRFs)

All relevant data collected during the study for all of the patients enrolled in the study shall be entered in the CRF by the responsible investigator or someone authorized by the investigator in a timely manner (as soon as possible after the information is collected) to ensure that they are clear and legible. The physician shall confirm the completeness, correctness, plausibility, and compliance with the ICH guidelines and the institutional SOPs of the data by dated signature. An explanation must be provided for any and all missing data. The entries shall be made with black ballpoint pen.

The properly filled in CRF will remain in the trial site; in case of electronic CRF, a copy of all pages will be conserved in the trial site.

15.3. Data Recording and Record Keeping

The investigator shall arrange for the retention of Essential Documents for the Conduct of a Clinical Trial (according to Chapter 8 of GCP ICH E6(R2) (e.g., patient files, other source data, and the Trial Master File) for at least 25 years after the completion or discontinuation of the study.

15.4. Data Protection

The researcher will have to keep the patient's original data and a copy of the signed written informed consent. The files will be kept in a locked closet in Nuclear Medicine Unit.

16. STATISTICS

16.1. Description of Statistical Methods

Diagnostic accuracies of 18F-PSMA PET and mpMRI will be calculated by means of sensitivity: true positive/(true positive + false negative); specificity: true negative/(false positive + true negative); PPV: true positive/(true positive + false positive); and NPV: true negative/(true negative + false negative) using the prostate biopsy result as reference standard.

- The assessment of quantitative imaging parameters, including radiomic features and conventional parameters, characterizing regions of csPCa will be performed by generalized Linear Mixed Models for binary responses. Logistic regression will be used for evaluating PET and MRI parameters and texture features in predicting the presence of csPCa, as defined by biopsy results. To assess the diagnostic performance of PET and MRI parameters, ROC curve analysis will be performed to select optimal cut-offs in predicting the presence of csPCa, as defined by cytological examination, and the corresponding diagnostic accuracy values will be computed.
- McNemar test will be used to compare the proportion of csPCa missed by 18F-PSMA PET or mpMRI alone (12).
- All statistical analyses and data processing will be performed using the R statistical package or the SPSS software. All p-value will be rounded to three decimal places. Statistical significance will be declared if the rounded p-value will be less than 0.050. Two-sided 95% confidence intervals will be calculated.

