Patients with both negative mpMRI and 18F-PSMA PET scan will receive a 12-core TRUS-Bx. Patients with only positive mpMRI will receive MRI-TBx and 12-core TRUSBx. Patients with only positive 18F-PSMA PET will receive 18F-PSMA PET-TBx and 12-core TRUSBx. MRI-TBx will be performed by means of a fusion software-assisted approach using the Biojet system taking 4 cores in any mpMRI suspicious areas. PSMA PET-TBx will be performed taking 4 cores in the area of the prostate showing an increased tracer uptake. All prostate biopsy specimens will be evaluated by fully dedicated uro-pathologist.

In order to calculate accuracy, sensitivity, specificity, positive predictive value and negative predictive value of 18F-PSMA PET/MRI for the identification of csPCa, 18F-PSMA PET/MRI findings will be correlated with histopathological samples gathered with prostate biopsy.

The proportion of csPCa missed by PSMA PET scan or mpMRI alone will be then calculated.

In order to study the proportion of unnecessary biopsies that could be spared by adding 18F-PSMA PET to mpMRI in the triage phase, only patients with positive mpMRI and negative 18F-PSMA PET scan will be considered for the analysis and the proportion of clinically insignificant PCa detected in this subset of patients will be assessed. In this way we will identify proportion of unnecessary prostate biopsies that could have been spared, thus reducing overdiagnosis.

Furthermore, the potential role of quantitative PET and mpMRI parameters in identifying csPCa will be investigated. Specifically, recently emerging radiomic features will be evaluated, together with PET- and MRI-derived quantitative conventional imaging parameters, and regression analyses will be used for evaluating their role in predicting histopathological data. To assess the diagnostic performance of PET and MRI parameters, ROC curve analysis will be performed to select optimal cut-offs in predicting the presence of csPCa as defined by cytological examination and the corresponding diagnostic accuracy will be computed (more detailed information in the section "Statistics" of this protocol). No interim analyses are planned.

The following measures will be taken in order to minimize the risk of bias:

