Biopsy protocol: Each patient will receive a 12-core random systematic biopsy (TRUSBx) and mpMRI targeted biopsy as standard clinical procedure. MpMRI software assisted targeted biopsy will be performed using the BioJet™ fusion system (D&K Technologies, Barum, Germany) (8,9). Before biopsy both the prostate and each mpMRI suspicious lesion will be contoured and superimposed with the transrectal (TR) ultrasound image. TR ultrasound will be performed using a Flex Focus 500 machine with a biplanar transducer (BK Medical, Herlev, Denmark) (10). In

addition, 18F-PSMA PET targeted biopsy will be also performed, using the BioJet™ fusion system relying on PET images co-registered with mpMRI images for a correct contouring of both prostate and 18F-PSMA PET ROIs and superimposition with ultrasound images. Each mpMRI and 18F-PSMA PET ROI will be biopsied with a 4-cores targeted biopsy. Prostate biopsies will be carried out using a 18-gauge needle and a biopsy gun providing a specimen size of 18-22 mm.

PET/MR quantitative analysis: ROIs on primary tumour showing 18F-PSMA uptake will be semi-automatically defined on transaxial PET images and the following semi-quantitative parameters will be extracted: maximum standardised uptake value (SUV_{max}), mean SUV (SUV_{mean}, using different thresholds and metabolic tumour volume (MTV) calculated at different thresholds. ROIs on the MR images, ADC and DCE maps will be drawn to measure MR parameters related to the lesions detected by MRI.

Radiomic analysis: Volumes of interest (VOIs) will be manually segmented on 18F-PSMA PET, T2w-images and ADC maps by expert Nuclear Medicine and Radiologist physicians in correspondence of the intra-prostatic findings referable to the site of primary tumour. IBSI compliant radiomic features (11) will be extracted from VOIs and features reduction and selection procedures will be used to define a smaller set of radiomic features showing the best discrimination between csPCa and clinically insignificant PCa or healthy tissue.

Remaining radio-pharmaceutical will be stored in a bunker at Ospedale San Raffaele and after radioactivity decay will be destroyed in accordance with the hospital and the applicable local, federal and national regulations.

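### Quantitative PET and MRI markers are scored in the same cohort that selects their cut-offs and features, with no internal validation specified; the primary and secondary endpoints are unaffected

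*Combined protocol and SAP*

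**What the plan says.** Section 8 adds a further investigation to the main design: "the potential role of quantitative PET and mpMRI parameters in identifying csPCa will be investigated". It refers the reader to the Statistics section for detail.

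Section 10.6 describes the measurements.
- PET: "ROIs on primary tumour showing 18F-PSMA uptake will be semi-automatically defined on transaxial PET images". SUVmean is taken at several thresholds, as is "metabolic tumour volume (MTV) calculated at different thresholds".
- MRI: regions "will be drawn to measure MR parameters related to the lesions detected by MRI".
- Radiomics: "features reduction and selection procedures will be used to define a smaller set of radiomic features showing the best discrimination", the contrast being csPCa against insignificant cancer or normal tissue.

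Section 16.1 describes the analysis. The assessment of quantitative parameters "characterizing regions of csPCa will be performed by generalized Linear Mixed Models for binary responses". Logistic regression relates PET and MRI parameters and texture features to csPCa on biopsy. Then "ROC curve analysis will be performed to select optimal cut-offs in predicting the presence of csPCa", "and the corresponding diagnostic accuracy values will be computed".

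The cohort is one centre and one arm, with 167 men. No section mentions a training/test split, cross-validation, a bootstrap or an optimism correction. Section 11.6 speaks of validation only in the sense of biopsy confirming imaging.

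**The concern.** A cut-off chosen because it separates the groups best in a dataset fits the noise in that dataset as well as the signal. Accuracy computed there at that cut-off is too high on average. Selecting features for best discrimination has the same effect, and it grows with the number of candidates. Trying several SUVmean and MTV thresholds adds further choices.

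At stake is what is published about these markers. Section 22 plans dissemination in the radiomics field, among others. A cut-off or signature reported with its apparent accuracy would be expected to perform worse in new men. With many candidate features, uninformative ones could look useful.

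**Working it through.** **1. The plan's own figure.** Section 16.2 assumes 56% prevalence and a sensitivity of 96% estimated to within 4 points at 95% confidence. Men with csPCa needed: 1.96² × 0.96 × 0.04 / 0.04² = 92.2, rounded up to 93. Total: 93 / 0.56 = 166.1, rounded up to 167. The figure reproduces. It was set for the precision of a sensitivity, not for model building. At 56%, 167 × 0.56 = 93.5, so about 94 men with csPCa and 73 without.

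**2. What has to be assumed.** The documents give no number of evaluable men or regions, no candidate count, no size of the selected set and no cut-off criterion. The simulations assume normal markers, independent units with one value each, and the Youden cut-off. Four group sizes (csPCa vs not) are used. 94 vs 73 is all 167 men. 120 vs 200 represents many comparison regions, for instance if normal tissue is sampled. 90 vs 40 and 80 vs 20 represent few, as could happen if only visible findings give values.

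**3. One marker, cut-off chosen in the data.** The marker is N(d, 1) with csPCa and N(0, 1) without, where d = √2 × Φ⁻¹(AUC). The apparent J = sensitivity + specificity - 1 is read off in the sample at the chosen cut-off c. The true J is Φ(d - c) + Φ(c) - 1. Mean excess of apparent over true, 5,000 runs per cell:

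| csPCa vs not | AUC 0.70 | AUC 0.80 | AUC 0.90 |
|---|---|---|---|
| 120 vs 200 | 0.050 | 0.042 | 0.034 |
| 94 vs 73 | 0.069 | 0.060 | 0.049 |
| 90 vs 40 | 0.088 | 0.078 | 0.064 |
| 80 vs 20 | 0.125 | 0.105 | 0.090 |

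At 94 vs 73 and AUC 0.70, J is 0.343 apparent and 0.274 true. Sensitivity is 66.8% against 63.7% (3.1 points) and specificity 67.5% against 63.6% (3.9 points). Over all sizes, apparent exceeded true in 79% to 91% of runs. For scale, the 95% half-width for 70% in 94 men is 1.96 × √(0.7 × 0.3 / 94) = 0.093.

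**4. Selected radiomic model, if accuracy is reported for one.** All features are pure noise (true AUC 0.50). The best five enter a logistic model, with 400 runs. Mean apparent AUC at 94 vs 73:

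| Candidates | 20 | 50 | 100 | 200 |
|---|---|---|---|---|
| Independent | 0.657 | 0.694 | 0.718 | 0.739 |
| Correlated 0.8 in blocks of 10 | 0.601 | 0.625 | 0.647 | 0.673 |

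For 20 to 200 independent candidates the range is 0.619 to 0.679 at 120 vs 200, and 0.745 to 0.855 at 80 vs 20.

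**5. Which correction works.** Best 5 of 100 independent features, selection repeated inside every fold or resample, 100 runs, 10-fold cross-validation and 60 bootstrap resamples:

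| Scenario | Apparent AUC | True | Cross-validation | Optimism-corrected bootstrap |
|---|---|---|---|---|
| Noise, 94 vs 73 | 0.716 | 0.500 | 0.505 | 0.581 |
| Noise, 80 vs 20 | 0.836 | 0.500 | 0.524 | 0.672 |
| Five real features (AUC 0.65 each), 94 vs 73 | 0.818 | 0.758 | 0.742 | 0.742 |
| Five real features, 80 vs 20 | 0.872 | 0.658 | 0.647 | 0.738 |

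The optimism-corrected bootstrap tests each resampled model on the full cohort, which contains the men it was built on, so it stays optimistic when selection is heavy. In further noise runs, out-of-bag scoring (only on men left out of the resample) and cross-validation both gave 0.50 to 0.51. Cross-validation with the cut-off chosen inside the folds gave a J near 0. Clustering of regions within men and mixed models were not simulated.

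**The case against.** **The analysis is peripheral.** It is absent from the synopsis objectives and from the section 6 table, and section 8 presents it only as a potential role. This stands, and it limits the weight of the point. But the protocol does not label the analysis exploratory: the exploratory row in section 6 concerns spared biopsies. Section 16.1 lists it with the other methods, under the same significance rule and confidence intervals.

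**The cut-off step may not cover radiomics.** In section 16.1 texture features appear in the logistic regression sentence, while the ROC sentence names only PET and MRI parameters. On that fair reading only step 3 of the working applies. The other reading is also open, because the same paragraph begins by counting radiomic features among the quantitative parameters. A reader might infer that the plan commits to reporting a radiomic signature with a grossly inflated AUC. The text does not say so, and the figures in step 4 are therefore conditional.

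**Validation is not excluded.** The unnamed selection procedures could include it. That is true, but nothing requires it, and validation with selection done outside the folds would not remove the bias.

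**The single-marker bias is smaller than the sampling error.** That stands for 94 vs 73: 3 to 4 points against a half-width of about 9. The bias is nevertheless systematic, and a confidence interval around the apparent value does not account for it.

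**Mixed models already deal with regions.** They address correlation within a man. They do not correct for choosing features or cut-offs in the data being scored.

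**Conclusion.** The point holds in a limited form. Sections 10.6 and 16.1 together choose features and cut-offs, and compute accuracy at the chosen cut-offs, in one cohort without a specified validation step. Followed as written, that accuracy is biased upward on average. For one marker at true AUC 0.70 to 0.90 the excess in sensitivity + specificity - 1 is about 0.07 to 0.05 if all 167 men give one value, and about 0.12 to 0.09 at an assumed 80 vs 20. For a selected multi-feature model, if its accuracy is reported, the bias can be large enough to make noise look informative.

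The direction follows from the method. The sizes rest on the assumed group sizes, candidate counts, normal markers and Youden criterion, and are illustrative.

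A reader might infer that the trial's headline accuracy is inflated too. The documents do not support that. The primary and secondary endpoints rest on a rule fixed in advance in sections 8 and 10.6 (PI-RADS 3 or above and/or focal uptake above background). None of them uses an estimated cut-off or a selected feature. The change is worth making, but the declared conclusions do not depend on it.

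**What to change.** In section 16.1:
- Label the quantitative and radiomic analysis exploratory. State its unit (man or region), the candidate parameters with their SUVmean and MTV thresholds, and the cut-off criterion. Say whether accuracy will be reported for a radiomic model.
- Estimate accuracy by cross-validation, or by bootstrap with out-of-bag scoring. Repeat feature selection, model fitting and cut-off choice inside each fold or resample, and keep all regions of one man together.
- Report these values beside the apparent ones, and describe the apparent ones as hypothesis-generating.
- Do not rely on the standard optimism-corrected bootstrap where features are selected from many candidates. On pure noise (best 5 of 100) it still returned about 0.58 at 94 vs 73 and 0.67 at 80 vs 20.

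The cost is computing time, a few lines of text and lower reported accuracy for these markers. No extra patients or procedures are needed.

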6. OBJECTIVES AND ENDPOINTS

Objectives	Endpoints	Time point(s)
Primary Objective To assess the accuracy and the predictive value of fully hybrid ^{18}F -PSMA PET/MRI for the diagnosis of csPCa	Primary Endpoint Diagnostic accuracies of ^{18}F -PSMA PET and mpMRI will be calculated by means of sensitivity: true positive/(true positive + false negative) and specificity: true negative/(false positive + true negative) using the prostate biopsy result as reference standard.	PET/MRI examination at day 0, and biopsy at day 1-30 (within a month from imaging study)
Secondary Objectives To compare the proportion of csPCa missed by ^{18}F -PSMA PET scan or mpMRI alone	Secondary Endpoints The proportion of csPCa (defined by analysis of prostate biopsy cores, ISUP grade equal or higher than 2) missed by PSMA PET scan or mpMRI alone will be calculated.	PET/MRI examination at day 0, and biopsy at day 1-30 (within a month from imaging study)
Exploratory Objectives To assess the proportion of unnecessary biopsies potentially spared	Other Number of clinically insignificant PCa (ISUP grade 1) identified combining mpMRI and ^{18}F -PSMA PET.	PET/MRI examination at day 0, and biopsy at day 90 (+/-90)

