8. TRIAL DESIGN

In this single-arm phase II, prospective, monocentric study we will test whether addition of 18F-PSMA PET scan to mpMRI helps improving the diagnostic pathway efficiency in identifying those men who should necessarily undergo TBx, because of high-risk to harbor csPCa.

Furthermore, the combined use of 18F-PSMA PET and mpMRI for the diagnosis of PCa may also result in a reduced number of follow-up procedures in those patients who can safely avoid a prostate biopsy given the very low risk of harboring csPCa using a single, one-stop approach with both imaging modalities. A more efficient pre-biopsy triage test using the fully hybrid 18F-PSMA PET/MRI might result in the reduction of the total number of biopsies for men with a clinical suspicion of PCa, reducing also patient discomfort combining two different diagnostic procedures in one single step and avoiding, whenever possible, the biopsy-related side effects.

A total of 167 consecutive patients with a clinical suspicion of csPCa (defined as the presence of PCa with ISUP grade equal or higher to 2), referred to simultaneous 18F-PSMA PET/MRI with mpMRI, will be identified and enrolled. PET/MRI images will be qualitatively and quantitatively evaluated by an experienced Nuclear Medicine and an experienced Radiologist physicians. In particular, for qualitative evaluation, lesions classified as PI-RADS higher or equal to 3 on mpMRI images and/or showing pathologically increased 18F-PSMA uptake on PET images, will be considered as positive for csPCa. All men will then receive a prostate biopsy (12-core random systematic prostate biopsy plus eventual targeted biopsy) as back-up histology according to the results of PET/MR imaging.

Specifically, patients with both positive mpMRI and 18F-PSMA PET, defined as the presence of one or more lesions with PI-RADS higher or equal to 3 and an increased uptake of 18F-PSMA, will receive a 12-core random systematic prostate biopsy (TRUS-Bx) in addition to MRI targeted biopsy (MRI-TBx) and 18F-PSMA PET targeted biopsy (PSMA PETTBx).

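### The ROC analysis names cytology, which the trial does not collect, as its reference, and the logistic and ROC analyses state neither a unit of analysis nor how several regions in one man are handled

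*Combined protocol and SAP*

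**What the plan says.** Section 16.1 describes three steps for the quantitative imaging parameters.

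- Parameters characterising regions of csPCa: the assessment "will be performed by generalized Linear Mixed Models for binary responses". No random effect is named.
- Regression: "Logistic regression will be used for evaluating PET and MRI parameters and texture features in predicting the presence of csPCa, as defined by biopsy results".
- ROC: "ROC curve analysis will be performed to select optimal cut-offs in predicting the presence of csPCa, as defined by cytological examination", with the accuracy at those cut-offs then computed.

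The same section promises two-sided 95% confidence intervals and a 0.050 significance threshold. Section 8 gives the ROC reference in the same terms: "in predicting the presence of csPCa as defined by cytological examination".

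Elsewhere the reference is biopsy tissue. The secondary endpoint in section 6 takes csPCa as "defined by analysis of prostate biopsy cores, ISUP grade equal or higher than 2". Section 8 has a uro-pathologist read all biopsy specimens and correlates imaging with histopathology. The schedule in section 11 lists prostate biopsy and no cytology.

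On the number of regions, section 8 defines a positive mpMRI by "one or more lesions with PI-RADS higher or equal to 3". Section 10.6 states: "Each mpMRI and 18F-PSMA PET ROI will be biopsied with a 4-cores targeted biopsy". That section also takes MR parameters from the lesions MRI detects, and seeks radiomic features that separate csPCa from insignificant cancer or healthy tissue.

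**The concern.** There are two separate points.

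The first is the reference standard. The text that governs the ROC analysis points to an examination the trial does not perform. It disagrees with the sentence directly before it and with the trial's own definition of csPCa. Anyone following section 16.1 literally has no data for the outcome variable.

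The second is the unit of analysis. Measurement and targeted biopsy are both done per ROI, so a data set with one row per ROI is available and is a natural one to analyse. The first step uses a mixed model, a type of method that can allow for correlated regions. The next two steps use methods that, in their ordinary form, treat rows as independent. If several rows come from the same man and are positively correlated, ordinary standard errors overstate the information. Odds ratios, AUC and cut-off accuracy would then carry intervals that are too short and p-values that are too small. With the unit left open, the choice between per-ROI and per-man results could also be made after the data are seen.

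**Working it through.** **The plan's own figure.** The documents give no number for the logistic, ROC or mixed-model analyses. The only figure in the statistics section is the sample size, and it reproduces: z² × 0.96 × 0.04 / 0.04² with z = 1.96 gives 92.2, rounded up to 93 men with csPCa; 93 / 0.56 = 166.07, rounded up to 167. It is a patient-level calculation for sensitivity, and neither point bears on it.

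**Reference standard, side by side.**

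| Place | How csPCa is established |
|---|---|
| 16.1, ROC sentence | cytology |
| 8, ROC sentence | cytology |
| 16.1, logistic sentence | biopsy results |
| 16.1, accuracy measures | prostate biopsy result |
| 6, secondary endpoint | biopsy cores, ISUP grade 2 or higher |
| 8, accuracy paragraph | histopathology from biopsy |
| 11, schedule | prostate biopsy only |

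The two ROC sentences stand alone. This part needs no arithmetic.

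**Clustering: a simple bound.** The documents give neither the mean number of regions per man (m) nor the within-man correlation (ICC), so both are assumed. With equal m, the design effect is DE = 1 + (m − 1) × ICC. An interval that ignores it is too short by 1 − 1/√DE, and its actual coverage is 2Φ(1.96/√DE) − 1.

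| m | ICC | DE | Interval too short by | Actual coverage |
|---|---|---|---|---|
| 1.0 | any | 1.00 | 0% | 95.0% |
| 1.2 | 0.1 | 1.02 | 1.0% | 94.8% |
| 1.2 | 0.7 | 1.14 | 6.3% | 93.4% |
| 1.5 | 0.1 | 1.05 | 2.4% | 94.4% |
| 1.5 | 0.7 | 1.35 | 13.9% | 90.8% |
| 2.0 | 0.1 | 1.10 | 4.7% | 93.8% |
| 2.0 | 0.7 | 1.70 | 23.3% | 86.7% |

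For example, at m = 2 and ICC = 0.7: 1 + 1 × 0.7 = 1.70; √1.70 = 1.304; 1 − 1/1.304 = 23.3%. This formula suits a proportion, such as sensitivity at a fixed cut-off. For an AUC it is only a rough guide.

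**Clustering: AUC by simulation.** Assumptions: 167 men, 1 + Poisson(m − 1) regions each, 56% of regions with csPCa, true AUC about 0.76, the same ICC for the marker and for csPCa status, and 1,500 runs per setting.

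| m | ICC | True SE | Ordinary SE | Ordinary coverage | Patient-clustered coverage |
|---|---|---|---|---|---|
| 1.2 | 0.3 | 0.0337 | 0.0339 | 94.5% | 94.5% |
| 1.2 | 0.5 | 0.0338 | 0.0338 | 94.4% | 94.8% |
| 1.5 | 0.3 | 0.0312 | 0.0303 | 93.2% | 93.7% |
| 1.5 | 0.5 | 0.0325 | 0.0304 | 92.1% | 93.6% |
| 2.0 | 0.3 | 0.0272 | 0.0262 | 93.9% | 94.7% |
| 2.0 | 0.5 | 0.0298 | 0.0261 | 91.5% | 94.2% |

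The simulation error of a coverage near 95% is √(0.95 × 0.05 / 1500) = 0.56 percentage points. At m = 1.2 the ordinary interval is therefore indistinguishable from a correct one. At m = 2 and ICC = 0.5 the ordinary SE is too small by 1 − 0.0261/0.0298 = 12%, against 18.4% from the design-effect formula at the same values.

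**The case against.** The strongest reply is that the plan never says the logistic and ROC analyses are run per ROI. Both predict the presence of csPCa, which can be read as one outcome per man; with one row per man there is no clustering. The logistic sentence can also be read as the logit form of the mixed model just before it. Section 10.6 places PET ROIs on the primary tumour and radiomic volumes at its site, which leans towards about one region per man for those measures; only the MR sentence speaks of lesions. The section 8 wording on one or more lesions defines a positive scan and does not describe an analysis data set. A PET and an MRI ROI on the same lesion need not be two rows either, since SUV and ADC can be two predictors on one row.

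Most of this stands. A reader might infer that the plan has chosen to ignore clustering and that its intervals will be too narrow. The text supports only an omission, whose effect depends on the unit and may be nil. The gap still remains on every reading. Per man, no rule says which of several regions supplies the value. As a mixed model, no patient effect is named, and the AUC and cut-off accuracy still have no clustered interval.

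On the reference, it is fair to say that cytology is probably a slip for histology and that the intended meaning can be recovered from neighbouring text. It still appears in both places that describe the ROC analysis. A reader might go further and argue that cytology could not yield an ISUP grade. The documents do not say so, and the contradiction does not need it.

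**Conclusion.** The reference-standard point holds outright: both ROC sentences name an examination the trial does not collect, contrary to its own definition of csPCa.

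The clustering point holds conditionally. It requires an ROI-level analysis, more than one ROI in some men, positive within-man correlation and ordinary standard errors. Under an assumed 1.5 to 2 ROIs per man and correlation 0.1 to 0.7, intervals are about 2% to 23% too short. For the AUC at correlation 0.3 to 0.5, ordinary coverage is about 91.5% to 94%. At one ROI per man the effect is zero, and at 1.2 it is small.

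Severity is minor. The quantitative and radiomic analyses appear in no objective or endpoint in section 6. It would be wrong to infer any consequence for the primary accuracy endpoint, the McNemar comparison or the sample size.

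**What to change.** 1. In sections 8 and 16.1, replace the cytology reference for the ROC analysis with histology of biopsy cores, ISUP grade 2 or higher.
2. In section 16.1, state for each of the mixed-model, logistic and ROC analyses whether the unit is the ROI or the man.
3. For ROI-level regression, use the mixed model with a patient random intercept, or GEE with patient as the cluster.
4. For ROI-level AUC, cut-offs and their accuracy, take 95% confidence intervals from a bootstrap that resamples men and keeps all ROIs of a sampled man together.
5. For per-man analyses, use one pre-stated value per man, for example the highest across his ROIs.

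The cost is a few sentences and a standard bootstrap, with no extra patients, procedures or data. The downside is slightly wider intervals where men contribute several ROIs. The changes should be made before the imaging parameters are linked to the biopsy results.
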